How the proposed research would add to existing knowledge. The proposed research will develop the BA protocol and measures and provide preliminary data for a larger-scale efficacy trial of BA. This line of research has the potential to add a powerful clinical tool for treating depression in VA rehabilitation settings and, thereby, improve access to an important form of care for veterans with post-TBI depression. Furthermore, the research has the potential to enhance community reintegration of veterans with TBI, the ultimate goal of rehabilitation and a critical priority for the VA health system.

1.3. Include rationale for including or excluding certain populations – in particular vulnerable populations.

We are not including vulnerable populations as defined by NIH.

2. Objectives

2.1. Describe the study's purpose, specific aims, or objectives.

The proposed pilot study is designed to test the feasibility of delivering BA for post-TBI depression in the VA rehabilitation setting. The specific aims are:

- **Aim 1: Assess feasibility in six domains.^{52,53}**
 - a) Acceptability: Acceptability to patients and staff, assessed using qualitative and quantitative measures.
 - b) Process: Recruitment; refusal and retention rates; study completion; eligibility criteria; and number of sessions attended.
 - c) Practicality: The resources of the rehabilitation setting that support the BA intervention and the constraints that may interfere. These will determine the probability that BA can be implemented.
 - d) Treatment safety: Number of adverse events, those related and unrelated to the study.
 - e) Participant comprehension of interview questions and intervention activities.
 - f) Research burden: Length of interviews, participant fatigue, need for breaks, and emotional distress.
- **Aim 2: Provide preliminary evidence of response, assessed using a pilot randomized controlled trial (RCT).** Evidence of response is also considered a feasibility focus. The pilot RCT will compare the BA group to a control group using a 2-group design (see figure below).

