4.1. Study Design

4.1.1. Describe experimental design of the study. Include sequential and/or parallel phases of the study, including durations, and explain which interventions are standard of care.

This feasibility study assesses feasibility in six domains and provides preliminary evidence of treatment response, through a pilot randomized controlled trial (RCT). The pilot RCT compares the intervention group (BA plus as Treatment as usual) with the control group (Treatment as usual). We will enroll 40 subjects (20 in each

group), conduct a baseline interview, randomize into the two groups, and then conduct a follow-up interview 3 months later. Subsequently, a qualitative phone interview to assess the experience of the intervention along with satisfaction/acceptability will be conducted with those in the intervention group. The BA intervention will be delivered in 6 sessions over 3 months by OTs trained in BA for post-TBI depression.

Procedure. At the baseline interview, the interviewer will review the study, answer veterans' questions, obtain Informed Consent, screen for depression using the CES-D scale and item 9 of the PHQ-9, and conduct the baseline interview battery. If the participant does not meet inclusion criteria based on the CES-D, and PHQ-9 at this time, they will not be included in the study as a randomized participant. We will thank them for their time, and they will receive compensation for the visit. They will also be offered referrals for services as appropriate.

Response cards presenting each question's response format will be employed to reduce response burden and facilitate interview progress. In previous studies, response cards were found helpful and acceptabl.^{47,48} The estimated time of the baseline interview is 1.3 hours, including time for Informed Consent. Interviews of this length have been conducted with veterans with TBI and depression in previous research and were not found excessively burdensome.^{47,48} The interview will be conducted in the setting preferred by the participant, a rehabilitation clinic office or his/her home. In our experience, most who complete the Baseline interview will be willing to continue to participate. Veterans who do not wish to continue with the study after the baseline interview will not be randomized or count towards our accrual goals.

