Within 48 hours of the baseline interview, eligible veterans will be randomized using the method of random permuted blocks (to control for possible changes over time in subject mix) and concealed allocation. Those randomized to BA will be contacted within 5 days by the interventionist and scheduled for the first session.

Those randomized to BA will receive the 6-session BA intervention (as well as treatment as usual [TAU]). Control participants will receive TAU only (which may include current medical and mental health treatments.) Three months after Baseline, a blinded interviewer will conduct the follow-up interview in

person or on the phone with all veterans. Subjects will be sent reminder letters two weeks prior to this 3-month follow-up interview.

Study instruments and when they are used are described in a table in Section 8 and included in the Appendices.

Study staff will offer to share findings with participants.

4.1.2. Include a description of how anticipated risk will be minimized and include an analysis of risk vs. potential benefit.

This study is designed for persons with TBI who have a CES-D score of 16 or greater at both screening and baseline. Such a score indicates the presence of clinically significant depressive symptoms. Those who answer affirmatively (1, 2, or 3) at the baseline interview to item 9 from the PHQ-9, indicating suicide ideation, will not be eligible for the study.

Because this study involves interviews with persons with TBI who have at least mild depression, there is a minimal risk that the interviews may contribute to emotional discomfort in the discussion of personal matters. In our previous study of veterans with TBI in their homes (the large majority of whom scored above the cutoff for clinical depression on the CES-D Short Form), using many of the same interview instruments as proposed, we encountered no upset or excessive fatigue with any participants nor did any adverse events occur as a result of study participation.

The study poses minimal risk to study participants, based on experience with our earlier in-home intervention study with veterans with TBI, the literature on rehabilitation interventions with persons with TBI, and literature on BA. The risk of burden or fatigue from the interview or intervention is also low.

Risks to privacy or subject discomfort about disclosing or considering sensitive information

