Quality of Life in TBI	The QoL-TBI ^{63, 64, 65, 66} is a 37-item patient-centered measure that captures the individual's perception of his/her health-related quality-of-life (HRQoL) in cognition, self-care, daily life and autonomy, social relationships, emotions, and physical problems. Baseline & Follow-up interviews.
Demographics & military characteristics	These characteristics are age, sex, years of education, race, Hispanic ethnicity, marital status, employment status, financial difficulty, combat exposure, and war cohort. Baseline interview.
Relevant health data	Years since most recent TBI, severity of TBI, co-morbidities, source of injury (e.g., blast exposure, vehicular, fall), number of TBIs, and history of prior TBIs and of depression. Baseline interview and PCRS review.
Post-Traumatic Stress Disorder	The 20-item PCL-5 ^{67, 68} is a self-report measure of PTSD symptom severity assessing 20 symptoms experienced in the past month that correspond to the DSM-V. Each item is rated on a 5-point Likert scale, from 1 (not at all bothered) to 5 (extremely bothered). A score between 31-33 indicates probable PTSD. ⁸⁶ Baseline interview.
Patient self-ratings of functioning	Self-rated competency in daily activities is measured using the Patient Competency Rating Scale (PCRS), ^{69,70} a 30-item standardized measure of patient competency designed for TBI populations. The stem question is, "How much of a problem have you had (in the past month) in ...?" The response format is a five-point Likert scale from 1 (cannot do) to 5 (can do with ease). Higher scores indicate better functioning. Baseline and Follow-up interviews.
Healthcare services utilization	Veterans with TBI may use outpatient and inpatient care, mental health services, social services, and military service-connected and/or disability services. This Checklist will assess frequency of use of 11 healthcare services in the past month and since the baseline. Baseline and Follow-up interviews.
Behavioral Activation	The 23-item Behavioral Activation for Depression Scale (BADS) ⁷¹ measures engagement in social and occupational activities hypothesized to underlie depression and targeted for change by BA, using 7-point Likert responses from 0 (not at all) to 6 (completely). Baseline and Follow-up interviews.

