Pain and self-rated health	Pain (frequency and intensity) and self-perceived health are especially germane to TBI and depression. These measures are taken from the SF36, ⁷² a well-established measure of health-related quality of life. Baseline interview.
COVID Impact	CAIR Pandemic Impact Questionnaire measures the physical, psychological, and financial impact of the COVID-19 pandemic ⁷³ Baseline and Follow-up interviews
Dose and Intensity	The Delivery Assessment form (Appendix 7) is completed by the OT- interventionist after each session, documenting start and stop times, treatment setting, TBI-related problems worked on, BA components used, and amount of time for each. These data will be used to characterize the intervention content. Each OT-intervention session.
OT-rated Acceptability	This 18-item Acceptability and Enactment Scale is part of the Delivery Assessment Form (Appendix 7) based on measures extensively used by the investigators. ³⁹ Final OT session.
Acceptability and experience of BA to participants	Measures of acceptability and perceived benefits from BA are collected in a final phone interview, immediately after the 3-month follow-up interview, with BA participants Appendix 9). Acceptability by patients – final phone interview.
Acceptability to clinic staff	Questions elicit clinic staff's thoughts about the feasibility and acceptability of a BA-based intervention in the rehabilitation clinic setting. Acceptability by staff – after completion of data collection.

9. **Data Analysis**

9.1. **Provide sample size determination and analysis (include anticipated rate of screen failures, study discontinuations, lost to follow-up etc.).**

This is a feasibility study using 40 subjects. It will assess recruitment, refusal, and retention rates and other indicators of feasibility as described earlier.

9.2. **Describe how, where and by whom the data will be analyzed.**

Data will be analyzed at the CMCVAMC by the PI and Co-Is.

Aim 1 will assess the feasibility of BA in the VA rehabilitation setting, following criteria suggested by Bowen et al.⁵² and Thabane et al.⁵³:

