Acceptability to veterans and staff, assessed using qualitative and quantitative measures. Qualitative: This analysis will be conducted for open-ended interview questions concerning the experience of receiving BA (for veterans) and the process of its implementation in the rehabilitation setting (for clinic staff). After verification of transcript accuracy for interviews, ATLAS.ti will be used to facilitate data organization, coding, and retrieval. Qualitative content analysis⁷⁴ will inductively generate codes and categories. Line by line coding will be conducted to identify codes or statements of meaning (level I coding) that are then grouped into larger categories (level II, coding for themes). Strategies to support scientific rigor will be followed: for credibility (member checking findings with a subsample of participants); dependability (audit trial); transferability (thick description); and confirmability (audit trial).⁷⁵

Quantitative: (1) On the Acceptance/Receipt Scale completed by the interventionist (final Delivery Assessment form), at least 75% should score ≥ 3.0 (Appendix 7); (2) On the Satisfaction Scale, administered to BA participants during the final interview (Appendix 9), $\geq 75\%$ should score ≥ 3.0 . (3) Willingness to participate in future related studies should be $\geq 75\%$. Criteria are based on our past study.⁴⁷

- (a) Process: (1) For recruitment, $\geq 50\%$, percent of veterans will be eligible to participate, and $\geq 30\%$ will be willing to participate. (2) For retention, $\geq 75\%$ of veterans in BA will attend ≥ 4 sessions, and $\geq 75\%$ will complete the study. (3) Less than 15% deviation from protocol on the Treatment Fidelity Checklist will occur.
- (b) Practicality: Resources of the rehabilitation setting that support the BA intervention and constraints that may interfere will assess the probability that BA can be implemented. Resources and constraints will be assessed by interventionists, the project manager, and clinic staff through discussions on issues including scheduling, coordination with other appointments, staff time, and space providing privacy.
- (c) Treatment safety: Number of adverse events (study-related and unrelated) will be monitored.
- (d) Eligibility criteria: The team will assess whether these criteria were too broad or restrictive.

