Subjects may be withdrawn from the study by the PI without their consent if the PI deems it in the best interest or safety of the subject, such as if the subject expresses suicidal ideation, or increased depression that would increase risk of suicide. The study PI or project manager will notify the subject directly and offer a safety visit (in person or over the phone) and referrals for other services. Subjects will not be withdrawn for changes in antidepressants or other medications affecting mood or behavior, or for changes in psychotherapy after consenting. Investigators will document the change(s).

10.2. Describe the consequences of a subject's decision to withdraw from the research and the procedures for orderly termination of participation by the subject (e.g., the subject contacting the investigator for an end-of-study visit).

The subject may withdraw at any time. Subjects will be offered a safety visit and referrals for other services to provide more support after an early withdrawal (by subject or investigator).

11. Reporting

11.1. Include procedures for reporting unanticipated problems, serious adverse events, and protocol deviations.

Adverse events, protocol deviations, and unanticipated problems will be collected at each study visit or intervention following the signing of the informed consent, or when the study team becomes aware of them. They will be reported to the IRB at the time of continuing review, or sooner, per IRB requirements, as necessitated by the type of event (e.g. SAE, serious unanticipated problem, protocol deviation impacting subject safety).

Data and Safety Monitoring Plan

[name] will be responsible for ensuring that the trial is conducted according to the protocol and will also be responsible for implementing the data safety and monitoring plan as described below. A data and safety monitoring plan is established to ensure the safety of all study participants and to ensure the validity and integrity of the data.

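### Treatment safety is an adverse event count collected at 7 scheduled points per BA veteran and 1 per control: report events by arm and source, and compare arms only on one common 3-month question

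*Combined protocol and SAP*

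**What the plan says.** Section 2.1, Aim 1(d), defines the domain: "Treatment safety: Number of adverse events, those related and unrelated to the study". Section 9.2, Aim 1(c), repeats it as the whole analysis: "Treatment safety: Number of adverse events (study-related and unrelated) will be monitored". Neither place mentions study arm, source of the report, denominator or threshold.

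Section 11.1 sets the collection rule: "Adverse events, protocol deviations, and unanticipated problems will be collected at each study visit or intervention following the signing of the informed consent", with the addition "or when the study team becomes aware of them".

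Section 4.1.1 fixes the contact schedule. For the intervention arm: "The BA intervention will be delivered in 6 sessions over 3 months by OTs trained in BA for post-TBI depression". Controls receive treatment as usual only. For both arms: "Three months after Baseline, a blinded interviewer will conduct the follow-up interview". Section 8.1, Table 2, adds a contact for the intervention arm alone, with acceptability measures "collected in a final phone interview, immediately after the 3-month follow-up interview, with BA participants".

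**The concern.** The collection rule is tied to study contacts, and the arms differ sharply in how many they have. A headache, fall or low spell in week 3 can be picked up at the next BA session. In a control veteran it must be remembered until month 3 or reach the team by chance. The recorded count therefore mixes how often events happen with how often someone asks.

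The pilot is meant to supply preliminary data for a larger efficacy trial, so its safety count is likely to be read by arm, if only informally. An excess in BA could then be taken as an effect of treatment when it partly reflects more frequent asking. Without the source of each event, a later reader could not separate the two.

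**Working it through.** The plan gives no safety figure to reproduce. The check is a count of collection points, followed by a test of what that count can and cannot establish.

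**Inputs.** 6 BA sessions, one 3-month interview (T2) in both arms, and 20 veterans per arm (section 4.1.1); collection at each visit or session (section 11.1); an attendance criterion of at least 4 sessions (section 9.2, Aim 1(a)).

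**Scheduled collection points after randomization**
- BA: 6 + 1 = 7 per veteran; 7 × 20 = 140 in the arm.
- Control: 1 per veteran; 1 × 20 = 20 in the arm.
- BA veteran attending only 4 sessions: 4 + 1 = 5, against 1.
- Counting the BA-only final phone interview: 7 + 1 = 8, against 1. The figure of 7 leaves it out and is the cautious one.

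**Direction.** Let c be the chance that the T2 interview captures an earlier event, and m the chance that every earlier BA session after the event missed it. Scheduled capture is c in control and 1 − m(1 − c) in BA. Since m ≤ 1, BA capture is at least c. This needs only that earlier asking does not lower capture at T2.

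**Size.** This needs c, which the documents do not give. As an illustration, assume evenly spaced contacts, events spread evenly over follow-up, independent capture with the same chance c at each contact, and no spontaneous reports. Then BA capture is the mean of 1 − (1 − c)^k for k = 1 to 7:

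| c (assumed) | BA capture | Control capture | Ratio |
|---|---|---|---|
| 0.9 | 0.984 | 0.9 | 1.09 |
| 0.5 | 0.858 | 0.5 | 1.72 |
| 0.3 | 0.694 | 0.3 | 2.31 |
| 0.1 | 0.329 | 0.1 | 3.29 |

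A second model, with contacts at weeks 2, 4, 6, 8, 10, 12 and 13 and recall that fades with time, gives 1.0 with perfect capture and recall. It gives 4.9 with 50% capture and a two-week recall half-life (0.537 / 0.110). The ratio is set by the assumption chosen, so none of these values is an estimate for this trial.

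**Spontaneous reports.** If a share s of events reaches the team unprompted in both arms, and d is BA capture at scheduled contacts, the ratio becomes [1 − (1 − s)(1 − d)] / [1 − (1 − s)(1 − c)]. It equals d/c at s = 0 and 1 at s = 1, so such reports pull it towards 1.

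**A remedy to avoid.** Comparing arms on events *first* recorded at T2 reverses the bias, because BA sessions have already removed most of them. Under the first model, BA capture at T2 is then the mean of c(1 − c)^(k − 1) over k = 1 to 7:
- c = 0.9: 0.143 / 0.9 = 0.16
- c = 0.3: 0.131 / 0.3 = 0.44
- c = 0.1: 0.075 / 0.1 = 0.75

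Asking afresh at T2 about all events since baseline gives c in both arms, a ratio of 1.0 if recall is equal.

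**The case against.** The strongest reply is that the plan never compares events between arms. It sets no test, threshold or progression rule on the count, so the bias belongs to an analysis that nobody has proposed. That stands as to severity: no stated result is wrong. It does not remove the point, because a two-arm pilot will be asked for events by arm, and the collection rule should be ready for that.

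Second, the count is already split by relatedness, and section 11 provides weekly review of alerts and events, with severity and cause examined if several occur. This is a real safeguard. But relatedness sorts only events that were recorded and cannot restore those a control veteran was never asked about.

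Third, safety data go beyond the count. PHQ-9 item 9 is asked at both interviews, with the Columbia scale after a positive answer. Alerts cover severe depression and suicidality. Service use is also recorded in both arms: "This Checklist will assess frequency of use of 11 healthcare services in the past month and since the baseline". A reader might infer that safety monitoring is inadequate; the documents do not support that. The gap concerns how the count is analysed.

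Fourth, Appendices 6 and 7 and the alert and adverse event forms are not in the public text. They may already hold a source field or a standard event question, so it cannot be said that these do not exist.

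**Conclusion.** The point holds as a cheap, low-severity improvement. The established part is the schedule, 7 collection points against 1, and the direction it implies: at equal true rates, a by-arm reading would tend to show more events in BA.

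Two stronger readings are tempting and not supported.
- A reader might infer that BA events will be inflated two- or three-fold. Such ratios come from assumed capture chances with spontaneous reports ignored. Section 11 also expects adverse events to be infrequent, so chance could outweigh any detection effect.
- A reader might infer that leaving individual CES-D worsening out of the safety analysis is a defect. Section 9.2, Aim 2, already inspects direction of change in CES-D by group on the same two measurements. An individual display is a choice of presentation.

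The conclusion rests on reading section 11.1 as written, with each BA session serving as a collection point, and on the absence of any equivalent scheduled contact in control before month 3.

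**What to change.** Amend sections 9.2, Aim 1(c), and 11.1 as follows.

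1. Report adverse events by arm, by relatedness and by where each was collected: OT session, T2 interview, final phone interview, or spontaneous report.
2. At T2, ask every veteran in both arms one standard question covering the whole time since baseline, whether or not an event is already on record. The blinded interviewer should ask it without sight of the event log.
3. Base any comparison of arms on the answers to that question alone. Label it descriptive, with no test.
4. Keep every session-collected event in the total count, counting once any event reported both at a session and at T2.

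Optionally, add a plot or listing of individual CES-D change by arm, with veterans lacking a T2 score shown separately.

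The cost is a few sentences, fixed wording for a question at an interview where events are already collected, and a source field in the event log if there is none. No visit, scale or staff is added.

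There are downsides. The comparison relies on three-month recall in veterans with TBI. Recall may differ between arms because BA veterans have been asked at earlier sessions. With 20 per arm and few events expected, the counts will be very small.

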Exclusion criteria are a diagnosis of severe TBI; psychosis; aphasia; history of bipolar disorder, history of severe physical aggressiveness, judged by the clinical team; or currently receiving CBT for depression. Veterans with severe TBI were judged unlikely to be able to fully engage in BA. Dementia will be an exclusion. Since no cutoff on standard dementia-screens is established for TBI populations, probable dementia will be determined on a case-by-case basis using physician diagnosis and difficulty understanding interview questions. A review of CPRS will confirm TBI diagnosis and severity.

8. Study Evaluations

8.1. Describe all evaluations to be conducted (including screening; tests/questionnaires that will be administered; any procedures that subjects will be required to complete) and data collection methods. Include materials as an appendix or separate attachment.

The table describes the constructs, the instruments that operationalize them, number of items, and when administered. Appendix 6 presents the baseline and 3 month follow-up interview batteries.

Table 2. Study constructs, measures, number of items, and when administered.

CONSTRUCTS	MEASURES
OSU TBI Short form	Ohio State University TBI Identification Method-Short form ⁵⁵ to confirm TBI diagnosis (OSU TBI-ID-SF) Baseline interview

Depressive Symptoms	The Center for Epidemiologic Studies Depression Scale (CES-D) is a well-established 20-item screening instrument that shows good psychometric properties in TBI populations. ^{56,57,58} Baseline & Follow-up interviews.
PHQ, question 9	The Suicide Ideation (Patient Health Questionnaire [PHQ-9], item #9) ⁵⁹ Baseline & Follow-up interviews.
Positive & negative affect	The 20-item Positive and Negative Affect Schedule ⁶⁰ (PANAS) is used to capture a wide range of emotions, allowing a broader examination of possible intervention effects beyond depressed affect. Baseline & Follow-up interviews.
Community Reintegration	The 17-item Participation Assessment with Recombined Tools-Objective (PART-O-17) ^{61, 62} is an objective measure of social functioning, developed from 3 existing CR measures to examine long-term outcomes and to evaluate intervention efficacy. ^{78, 79} Baseline & Follow-up interviews.

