- (e) Participant comprehension: Interviewer and interventionist will note areas of participant difficulty understanding interview questions and intervention activities. Missing data will also reflect difficulty.
- (f) Research burden: Length of time to complete interviews will be recorded using start and stop time data on the interview. The interviewer will record participant fatigue, wish to take breaks, and/or emotional distress.

Aim 2 will assess change in participant response by comparing Group 1 (BA + TAU) and Group 2 (TAU) on outcomes at T2 (3-month follow-up). We will first conduct

descriptive analyses separately for the BA and control groups to characterize the sample and assess the success of randomization in balancing the two groups. We will inspect trends, directions of change in the two groups, and associations between baseline characteristics (T1) and CES-D scores at follow-up (T2). The same trends and changes will be inspected for the secondary outcomes of CR and QOL. Analyses will be conducted using SPSS version 25.

Aim 3 is to develop and refine the BA protocol, manual, and interview measures. In the first 3 months, an expert panel comprising the investigators, interventionists, interviewer, clinic staff, and two veterans with TBI will review and modify the existing protocol and manual to adapt them for hallmark deficits of TBI. The panel will meet monthly to monitor the study, assessing need for additional compensatory strategies and removal or alteration of strategies that depend on: abstract thinking; patients' understanding of TBI-related depression; awareness of emotion and its regulation; and interpersonal issues. Interview measures will be assessed for participant comprehension, sensitivity, and burden. This pilot study will produce a refined BA protocol and manual for post-TBI depression whose efficacy will be evaluated in a larger RCT.

An Exploratory Aim will examine engagement in activity as the mechanism underlying effects of BA. Although mediation analysis is beyond the scope of this feasibility study, we will explore characteristics of activity engagement using the BADS and its associations with the BA intervention and with depression.

10. Withdrawal of Subjects

10.1. Describe any anticipated circumstances under which subjects will be withdrawn from the research without their consent.

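### Aim 2 compares the arms at follow-up but commits to no baseline-adjusted difference and no confidence interval

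*Combined protocol and SAP*

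**What the plan says.** Section 2.1 gives the purpose of Aim 2: "Provide preliminary evidence of response, assessed using a pilot randomized controlled trial (RCT"). Section 1.2 adds that the study should supply preliminary data for a larger efficacy trial.

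Section 9.2 holds the whole quantitative plan for this aim:

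- The comparison: "Aim 2 will assess change in participant response by comparing Group 1 (BA + TAU) and Group 2 (TAU) on outcomes at T2".
- Descriptive analyses by arm come first, in part to "assess the success of randomization in balancing the two groups".
- For CES-D: "We will inspect trends, directions of change in the two groups, and associations between baseline characteristics (T1) and CES-D scores at follow-up (T2").
- For the other two outcomes: "The same trends and changes will be inspected for the secondary outcomes of CR and QOL".

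The baseline value of each outcome is collected. Section 8.1 states: "Appendix 6 presents the baseline and 3 month follow-up interview batteries". Table 2 there schedules CES-D at both interviews. It does the same for PART-O-17, described as "developed from 3 existing CR measures to examine long-term outcomes and to evaluate intervention efficacy", and for QoL-TBI, whose entry ends "social relationships, emotions, and physical problems. Baseline & Follow-up interviews".

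Three other statements set the context. Section 2.2 declares hypotheses not applicable. Section 9.1 presents the 40 subjects as a feasibility number. Section 4.1.1 plans 20 per arm, with concealed allocation in random permuted blocks and no stratification on CES-D mentioned.

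**The concern.** The arms are to be compared at T2, but the plan does not say what number will express the comparison or how its uncertainty will be shown. Baseline scores serve to describe balance and associations. They do not enter the between-arm contrast, and nothing is said about what follows if balance turns out poor.

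Two things are at stake.

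- **Use of the result.** Having no hypotheses excuses the absence of a test. It does not excuse presenting a difference between about 40 people without an interval. Whoever plans the efficacy trial will want that interval, the residual SD and the correlation of each outcome with its own baseline. The CES-D correlation may fall within the planned T1-T2 associations. The rest is not committed to.
- **Choice of estimate.** Aim 2 is framed as change, compared at T2, with directions of change inspected by arm. The plan names no between-arm difference in change. A reader may still form one, and it can point the other way from the T2 difference. Naming one estimate in advance settles which is reported.

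**Working it through.** **Inputs.** From the documents: 20 per arm (4.1.1), and a 75% completion criterion in a sentence about BA (9.2). Applying that criterion to TAU as well is an assumption. Assumed, because the documents give neither: CES-D SD 10 (range 8 to 12), and a baseline-T2 correlation r among enrolled participants of 0 to 0.6. There is no stated precision or power to reproduce, since 40 is given without an effect size, SD or error rate.

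**Formulas**, with N = n1 + n2:

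- Unadjusted 95% half-width = t(N−2) × SD × √(1/n1 + 1/n2).
- Adjusted 95% half-width = t(N−3) × SD × √(1−r²) × √(1/n1 + 1/n2) × √(1 + 1/(N−4)). The last factor is the expected cost of estimating the baseline slope.

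**At 20 + 20.** Unadjusted: 2.0244 × 10 × √0.1 = 6.40. Adjusted at r = 0: 2.0262 × 10 × √0.1 × √(1 + 1/36) = 6.50. Other values of r multiply 6.50 by √(1−r²).

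| Arms | Unadjusted | r = 0 | 0.1 | 0.2 | 0.3 | 0.4 | 0.5 | 0.6 |
|---|---|---|---|---|---|---|---|---|
| 20 + 20 | 6.40 | 6.50 | 6.46 | 6.36 | 6.20 | 5.95 | 5.63 | 5.20 |
| 15 BA + 20 TAU | 6.95 | 7.07 | 7.03 | 6.93 | 6.74 | 6.48 | 6.12 | 5.66 |
| 15 + 15 | 7.48 | 7.63 | 7.60 | 7.48 | 7.28 | 7.00 | 6.61 | 6.11 |

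At 20 + 20 the adjusted interval is 1.5% wider at r = 0, 3% narrower at r = 0.3 and 19% narrower at r = 0.6. At 15 + 15 it runs from 2.1% wider to 18% narrower.

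**Break-even.** Setting the two half-widths equal gives r² = 1 − [t(N−2)/t(N−3)]² / (1 + 1/(N−4)). This yields r = 0.170 (20 + 20), 0.183 (15 + 20) and 0.201 (15 + 15).

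**Other SDs, 20 + 20.** For SD 8 to 12 the unadjusted half-width is 5.1 to 7.7. Adjusted, it is 5.0 to 7.4 at r = 0.3 and 4.2 to 6.2 at r = 0.6. In SD units, which also serve PART-O-17 and QoL-TBI, it is 0.64 unadjusted, and 0.65, 0.62 and 0.52 adjusted at r = 0, 0.3 and 0.6.

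**Simulation** (40,000 trials per setting, 20 + 20, bivariate normal, complete data). The adjusted interval is the narrower one in 20%, 27%, 47%, 69%, 87%, 96% and 99% of trials at r = 0, 0.1, 0.2, 0.3, 0.4, 0.5 and 0.6. Its coverage is 0.948 to 0.953.

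**Chance imbalance.** The baseline difference has standard error √(2/20) = 0.316 SD. The probability that it exceeds 0.3 SD in either direction is P(|Z| > 0.3/0.316) = 0.343, and its mean size in those trials is 0.469 SD. The unadjusted T2 difference then shifts on average by r × 0.469 × 10, which is 0.5, 0.9, 1.4 and 2.8 points at r = 0.1, 0.2, 0.3 and 0.6. After adjustment the simulated mean shift is −0.05 to 0.02 points.

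**T2 level against change.** With a true benefit of 0.3 SD (3 points at SD 10), the T2 difference and the difference in change have opposite signs in 19% to 20% of simulated trials across r = 0 to 0.6.

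**The case against.** The strongest reply is that nothing in the plan is wrong. This is a pilot without hypotheses, response is itself treated as a feasibility matter, and efficacy is left to a later trial. Description is a legitimate choice, and the source is a protocol summary taken from an ethics form, where modelling detail may be sparse. All of that stands, and it is why the point is an improvement only.

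The precision gain is also small near the threshold. At r = 0.2 the half-width moves from 6.40 to 6.36, and the adjusted interval is the narrower one in fewer than half of trials. The requirement of CES-D 16 or more at both screen and baseline (7.1) restricts the baseline range and may lower r for CES-D. The figures at r = 0.6 have no support in the documents. This stands too. PART-O-17 and QoL-TBI have no such floor.

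Chance imbalance is not a further loss on top of imprecision: over all trials the shift averages zero and its variability is already inside the ±6.4. That is correct. The shifts above only show what adjustment does in the third of trials where imbalance occurs. The 20% sign disagreement arises only if someone also reads the arms on change. The unadjusted and adjusted T2 differences disagree in sign less often, in about 3% to 12% of trials over r = 0 to 0.6.

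Finally, adjustment does not deal with missing follow-up. Section 10.1 allows withdrawal for suicidal ideation or increased depression, so missingness may depend on outcome. A 95% interval can also be read as a test. Both are limits of the remedy, but the planned T2 comparison has the first as well.

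None of this supplies the missing estimate or interval. Inspecting associations between baseline characteristics and T2 scores is not a baseline-adjusted contrast between arms.

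**Conclusion.** The concern holds as a low-cost improvement. The documents commit to no adjusted between-arm estimate and no interval for any of the three outcomes, although each outcome's own baseline is collected.

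Adjustment narrows the interval on average once r exceeds about 0.2 (0.17 with full follow-up). The gain is 3% to 19% for r between 0.3 and 0.6, and the loss is about 2% at worst. The estimate stays imprecise either way: at 20 per arm, more than half an SD on each side over the range of r shown. Reporting the interval is worthwhile at any r.

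The sizes rest on an assumed SD and r, equal SDs in the two arms, a roughly linear baseline-T2 relation and approximate normality.

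**What to change.** Add to the Aim 2 text in Section 9.2:

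- For CES-D, PART-O-17 and QoL-TBI, report the between-arm difference at T2 from a linear model with arm and that outcome's own baseline value, with a 95% CI. Include all randomised participants with T2 data, by assigned arm. Present it as estimation, without a hypothesis test.
- For each outcome, report the residual SD and the correlation between baseline and T2.
- Keep the inspection of trends and directions of change, labelled as descriptive.

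The cost is two or three sentences and one linear model per outcome in the SPSS version already named. It needs no new data, visits or participants. The downside is one degree of freedom, and an interval 1.5% wider (20 per arm) to 2.1% wider (15 per arm) if baseline and T2 are uncorrelated.
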